4.2 Outcome Measures

4.2.1 Primary Outcome Measures

The primary outcome measure for this study is:

- Mean change in the specificity, quantity and quality of serum antibody titers to the vaccine viruses, pH1N1, H3 and influenza B using HAI (year 1-5) and MN for pH1N1 and H3 viruses (years 1-5 from Day 0 to Day 28)

- Mean change in the CD4 T cell reactivity to pools of total pHA peptides derived from the pH1N1 HA, as well as H3, influenza B HA, NP, and M1 peptides will be quantified using cytokine Elispot From Day 0 to Day 14

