12 STATISTICAL CONSIDERATIONS

12.1 Study Hypothesis

The primary hypothesis being tested in this study is that there will be differences in the serum antibody response, specificity, quantity and quality of memory B cell derived polyclonal antibodies (MpAb) and specificity and magnitude of the HA-specific CD4 T cell response between recipients of egg-derived and recombinant vaccines.

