12.2 Sample Size Considerations

The power analysis is based on the primary aim of comparison of serum antibody, specificity, memory B cell derived polyclonal antibodies (MpAb) and HA-specific CD4 T cell counts (in log scale to stabilize variance) between the group of subjects vaccinated with egg derived TIV IM and the group of subjects vaccinated with Baculovirus derived TIV IM. In this explorative study, the HA-specific CD4 T cell response to the Baculovirus derived vaccine is unknown and thus no information is available about the group difference. But our past experience indicated the coefficient of variation (CV) of HA-specific CD4 T cell counts varied between 0.25 and 0.4 [18]. If we assume CV and use percent-change differences in HA-specific CD4 T cell counts relative to the group with egg derived vaccine, with 45 subjects per group, we will have 80% power to detect at least 10% ~ 20% difference in HA-specific CD4 T cell counts between the two groups. This power analysis is based on two-sample t test with a two-sided significance level of 0.05 and equal allocation of subjects to any two groups.

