12.4 Final Analysis Plan

We will define the groups as: G1 (egg derived vaccine) = G1a (seronegative to pH1N1 virus and receiving egg derived vaccine) + G1b (seropositive and receiving egg derived vaccine); G2 (baculovirus derived vaccine) = G2a (seronegative to to pH1N1 virus and receiving baculovirus derived vaccine) + G2b (seropositive and receiving baculovirus derived vaccine). The log transformation will be applied to stabilize variance, as suggested by our past experience [18]. The between-group and among-group comparison in each of the outcomes will be based on both standard statistical analysis approaches using summary statistics and the complicated random variance model approach. Specifically, each of CD4 specific cells for different Influenza proteins (eg HA, NP etc), memory B cell derived polyclonal antibodies, HAI and MN titers among the four groups and between G1 and G2, between G1a and G2a, and between G1b and G2b, we will use maximum responses or maximum boost responses (maximum value after day 0 – value at day 0) or maximum fold increase as endpoint and do group comparison by ANOVA for among-group comparison and two-sample t-test for between-group comparison, or their nonparametric analogy of Kruskal-Wallis test and Wilcoxon Rank sum test, respectively, may also be applied for robustness. Multiple comparisons may subject to Bonferroni correction, if appropriate. Correlation test such as Pearson correlation analysis, or its nonparametric analogy of Spearman correlation analysis, will be used to study how baseline CD4 responses and/or memory B cell derived polyclonal antibodies, HAI, MN titers affect the boost responses of CD4, memory B cell derived polyclonal antibodies, HAI and MN titers after vaccination.

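### About ten primary measures are tested with optional Bonferroni and no defined family or success rule, while the 80% power covers one CD4 comparison at an uncorrected 0.05

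*Combined protocol and SAP*

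**What the plan says.** **Primary measures (Section 4.2.1).** The first item covers change from Day 0 to Day 28 in "serum antibody titers to the vaccine viruses, pH1N1, H3 and influenza B" by HAI, with MN for pH1N1 and H3. The second covers change from Day 0 to Day 14 in CD4 ELISPOT reactivity to five pools: pH1 HA, H3, influenza B HA, NP and M1.

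**Hypothesis (Section 12.1).** It expects differences between egg-derived and recombinant vaccine in three domains joined by the word *and*: serum antibody, memory-B-cell-derived polyclonal antibody (MpAb) and HA-specific CD4 response. MpAb is not among the outcome measures in Section 4.2.

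**Power (Section 12.2).** "with 45 subjects per group, we will have 80% power to detect at least 10% ~ 20% difference in HA-specific CD4 T cell counts", given that "the coefficient of variation (CV) of HA-specific CD4 T cell counts varied between 0.25 and 0.4". The basis is "This power analysis is based on two-sample t test with a two-sided significance level of 0.05 and equal allocation of subjects to any two groups". The section names antibody and MpAb as part of the same primary aim but gives power only for CD4 counts. It also calls the study explorative.

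**Analysis (Section 12.4).** Each outcome is compared among four vaccine-by-serostatus groups and in three pairwise contrasts, using one of three endpoint forms (maximum, maximum boost or maximum fold increase). On multiplicity: "Multiple comparisons may subject to Bonferroni correction, if appropriate".

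**The concern.** The plan lists many primary measures and leaves open whether correction applies, over which tests, and what pattern of results would count as support for the hypothesis. The one power figure assumes no correction.

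These choices would be made with data in view. Assignment is open label (Section 5) and immunogenicity is analysed yearly (Section 12.3.2). Section 3.2 already reports first-year HAI results that favour the recombinant vaccine. A reader of the final report could not tell what error rate attaches to a claimed difference, and the stated power would not apply if the optional correction were used.

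**Working it through.** **1. Count of measures (from Section 4.2.1).** HAI 3 + MN 2 + CD4 pools 5 = 10. Counting the two influenza B lineages in the Section 3.1 vaccine table separately for HAI gives 11.

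**2. The plan's own power figure.** Inputs from Section 12.2: n = 45 per group, two-sided 0.05, 80% power, CV 0.25 to 0.4. I treat the CV as the between-subject SD of the analysed quantity relative to its mean.

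- Normal approximation: d = (1.960 + 0.842) × √(2/45) = 0.591 SD.
- Noncentral t, with df = 88 and noncentrality d × √(45/2): d = 0.597 SD.
- Raw scale: 0.597 × 0.25 = 14.9% and 0.597 × 0.4 = 23.9%.
- Section 12.2 refers to the log scale. With SD = √ln(1 + CV²), the SDs are 0.2462 and 0.3853. The detectable increase is 15.8% and 25.9%, and the detectable decrease is 13.7% and 20.6%.

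Taken the other way, power at the stated differences is:

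- 10% at CV 0.25: d = 0.40, power 47% (44% to 52% on the log variants).
- 20% at CV 0.4: d = 0.50, power 65% (60% to 78% on the log variants).

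The upper end is nearly met on one reading, a log-scale decrease. The lower end of 10% is met on none.

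**3. Chance of at least one false positive.** This assumes one contrast, ten measures each at 0.05, no true differences, and support claimed from any one measure. If independent: 1 − 0.95^10 = 40.1%. The correlated cases come from simulating two-sided z tests with a common correlation.

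| Assumed correlation | 10 measures | 11 measures |
|---|---|---|
| 0 | 40% | 43% |
| 0.3 | 35% | 37% |
| 0.5 | 29% | 30% |
| 0.7 | 21% | 22% |
| 0.9 | 13% | 13% |

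The documents give no correlations. Choosing among the endpoint forms and contrasts in Section 12.4 could only add to these figures.

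**4. Power if Bonferroni is applied.** Start from d = 0.597, which has 80% power at 0.05 with 45 per group (noncentral t throughout).

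| Tests in family | Level | Power | SD detectable with 80% power | n per group to keep 80% |
|---|---|---|---|---|
| 1 | 0.05 | 80% | 0.597 | 45 |
| 2 | 0.025 | 71% | 0.659 | 55 |
| 3 | 0.0167 | 65% | 0.694 | 61 |
| 5 | 0.010 | 58% | 0.734 | 68 |
| 10 | 0.005 | 48% | 0.787 | 77 |
| 11 | 0.00455 | 47% | 0.794 | 78 |

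**5. Restated difference for a family of two.** At two-sided 0.025, raw scale: 0.6594 × 0.25 = 16.5% and 0.6594 × 0.4 = 26.4%. On the log scale, exp(0.6594 × 0.2462) − 1 = 17.6% and exp(0.6594 × 0.3853) − 1 = 28.9% for an increase. For a decrease, 1 − exp(−0.1623) = 15.0% and 1 − exp(−0.2541) = 22.4%.

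**The case against.** Several stronger conclusions are tempting, and the documents do not carry them.

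- **That any single difference confirms the hypothesis.** Section 12.1 joins the domains with *and* and gives no success rule. If every measure had to differ, there would be no inflation of error, although joint power would be low: 0.8^10 = 10.7% if independent. The defect is the missing rule, not a lax one.
- **That 80% power and a 5% error rate are incompatible.** A single designated primary test, or a fixed sequence starting with HA-specific CD4, would keep 0.05 for that test. The plan contains neither, but it also never promises 5% family-wise error, and the Section 12.2 figure is a per-comparison one.
- **That the plan is wrong about a third of the time.** That figure needs an assumed correlation of roughly 0.3 to 0.5. HAI and MN against the same virus in the same sera could be far more strongly correlated.
- **That the count is fixed at 11.** Ten follows from Section 4.2.1. Eleven needs influenza B split by lineage, which that section does not do. NP and M1 are listed as primary measures but are not HA-specific, so they do not bear directly on the hypothesis in Section 12.1. Leaving them out gives eight measures, and 1 − 0.95^8 = 34% if independent.

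The explorative label also deserves weight. It excuses the absence of strict error control, but it sits beside a declared primary hypothesis and a claim of 80% power at 0.05. Finally, the rank tests in Section 12.4 can fairly be read as sensitivity analyses and are not counted above.

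**Conclusion.** The point holds as a gap in specification. About ten primary measures have no named family, no success rule and only discretionary correction, and the stated power covers one of them at an uncorrected level.

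The size depends on the rule eventually adopted. Under an any-measure rule without correction, the false-positive chance is 13% to 40% for ten measures in one contrast. With Bonferroni for ten, a difference that had 80% power has about 48%. Both figures assume 45 evaluable subjects per group. The first also rests on assumed common correlations.

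Separately, the 10% to 20% range is optimistic even before correction: on the raw scale it is about 15% to 24%.

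**What to change.** In Section 12.4, replace the optional sentence with wording such as: *The primary comparison is recombinant versus egg-derived vaccine. The primary family is (1) log change in pH1N1 HAI titer, Day 0 to 28, and (2) log change in pH1 HA-specific CD4 ELISPOT, Day 0 to 14. These are tested by the Holm procedure at two-sided 0.05. All other measures, endpoint forms and contrasts are supportive.* The two measures are an example. Both already stand in Section 4.2.1, one per primary objective, and the investigators may prefer others. The text should also say which egg-derived product or products form the comparator, and what result counts as support for the hypothesis.

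Mark the remaining measures in Section 4.2.1 as supportive, and make Sections 12.1 and 4.2 agree on the status of MpAb.

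In Section 12.2, restate the detectable difference at the Holm first-step level of 0.025: about 0.66 SD, or 16.5% at CV 0.25 and 26.4% at CV 0.4 on the raw scale, with the scale named. Quoting 71% power alone would mislead, because it refers to 0.597 SD. At the 10% and 20% now written, raw-scale power at 0.025 is about 36% and 54%.

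The cost is a less favourable stated figure and fewer measures carrying a confirmatory claim: MN and the other CD4 pools would lose that status. No extra subjects, samples or assays are needed.

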3.3 Rationale

Our observations to date lead to the following model: Traditional egg-derived TIV have contaminating internal virion proteins that preferentially elicit memory CD4 T cells specific for these proteins. These CD4 T cells will have limited efficacy as helpers for the neutralizing Ab response and will suppress the CD4 T cell response to new HA epitopes in the vaccine. The current study will test this hypothesis by comparing CD4 cell responses to specific epitopes, and the subsequent B cell and antibody response, in subjects receiving a vaccine containing only HA protein to vaccines with more complex antigenic characteristics. The CD4 T cell reactivity to pools of unique, conserved, and total pH1 HA peptides as well as H3, influenza B HA, NP, and M1 peptides will be quantified using cytokine Elispot assays and flow cytometry, and then compared to the subsequent antibody and B cell response.

We will also use this study as an opportunity to evaluate the effects of prior vaccination. Recent studies have emphasized the potential negative effect of vaccination in prior years on both the immune response as well as the protective effectiveness of current vaccine. In order to evaluate this phenomenon in the context of multiple vaccine formulations, we will ascertain the prior vaccination history of the subjects and stratify vaccination based on vaccine history.

In addition, subjects who participated in this study in a previous year are eligible to re-enroll, and will receive the same vaccine that they were randomized to previously. This will allow an evaluation of differences between vaccine formulations in the responsiveness to multiple vaccinations.

Furthermore, recent studies indicate reports that the glycosylation pattern of viral hemagglutinins produced in cell culture can vary depending on the host cell used [11, 12], and that this can affect CD4 T cell immunogenicity and antibody recognition. As a cell culture-based influenza vaccine production platform offers many advantages and may eventually supplant the traditional egg-based approach, it is of great value to understand the CD4 T cell response induced by this vaccine and how this affects neutralizing Ab production.

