8.2 Vaccination (Defined as Day 0)

Subjects will be considered enrolled if they have signed the consent form. However, only subjects who met the entry criteria will be vaccinated and followed. Note that the screening visit and the vaccination visit may take place on the same day. At the vaccination visit the following procedures will be performed.

- An interim medical history will be obtained (unless the screening and vaccination visit are the same) including concomitant medications, detailing any subsequent medical events the subject has experienced since the screening visit.
- A directed physical exam will be performed, if indicated by the interval history, directed at the relevant portions of the exam.
- A urine pregnancy test will be obtained in female subjects. This test must be negative for the subject to continue in the study.
- The entry criteria will be reviewed with the subject and it will be verified that the subject continues to meet the entry criteria.

- A serum sample will be obtained from an arm vein for baseline antibody titers
- A sample of Peripheral Blood Mononuclear Cells (PBMC) will be obtained for assessment of baseline influenza-specific B cells and CD4 cells
- Subjects that were not vaccinated with influenza vaccine with the prior year's vaccine, will be randomized at the pharmacy into one of the three (FluBlok, Fluzone SD, Fluzone HD) vaccine groups, and will receive the indicated vaccine by intramuscular injection in open label fashion.
- Repeat subjects will receive the same vaccine they received previously. (FluBlok, Fluzone SD, Fluzone HD, Flucelvax)
- Subjects will be observed in the clinic for 30 minutes post vaccination for development of acute adverse events

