9.2 Laboratory Evaluations/Assays

9.2.1 Immunogenicity Evaluations

Serum hemagglutination-inhibition (HAI). HAI will be performed in microtiter format using turkey RBCs and egg-grown, betapropiolactone-inactivated A/California/07/09 virus as antigen. The titer of antibody will be defined as the highest dilution resulting in complete inhibition of hemagglutination. Sera will be treated with receptor-destroying enzyme and heat inactivated prior to testing at an initial starting dilution of 1:4. Sera with no detectable HAI titer will be assigned a titer of 1:2 for calculation purposes.

Microneutralization (MN) assay: Sera will be tested by microtiter technique for neutralization of an A/California/07/09 x PR8 reassortant virus in MDCK cells. Viral growth will be determined by ELISA of the cells following fixation with methanol using a combination of M- and NP-specific monoclonal antibodies. The titer of antibody will be defined as the highest titer resulting in 50% inhibition of antigen signal compared to un-neutralized control wells. Sera will be treated with RDE and heat inactivated prior to testing at an initial starting dilution of 1:10. Sera with no neutralizing titer will be assigned a value of 1:5 for calculation purposes.

B cell responses: Peripheral Blood Mononuclear Cells (PBMC) will be obtained before and on day 7 and 28 after vaccine and evaluated for B-cell responses. B cell responses will be evaluated by memory cell assay [16] and antibody secreting cell assay. In addition, B cells will be cultured in vitro and the functional quality of secreted antibody assessed by HAI and MN assays

CD4 T cell responses: PBMCs collected prior to and on day 3, 7, 14 and 180 after vaccination will be evaluated for the presence of antigen specific CD4 cells by ELISPOT assay and flow cytometry using a panel of peptides spanning the H1 hemagglutinin, neuraminidase and internal virion proteins such as NP and M1 [17]. This assay will identify both cross reactive and H1 specific epitope responses, as well as recall of memory cells to conserved internal virion proteins. PBMC will also be evaluated for the presence of antigen specific ELISPOT and cell homing markers by flow cytometry.

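### For same-marker pairs, the Section 12.4 correlation of baseline with boost has the wrong null: the Day 0 value is both the predictor and the quantity subtracted from the outcome

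*Combined protocol and SAP*

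**What the plan says.** Section 12.4 defines its response measures as maximum responses, "maximum boost responses (maximum value after day 0 – value at day 0) or maximum fold increase as endpoint", and states that "The log transformation will be applied to stabilize variance". On the log scale a boost and a log fold increase are the same difference.

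The section then plans a "Correlation test such as Pearson correlation analysis, or its nonparametric analogy of Spearman correlation analysis", which "will be used to study how baseline CD4 responses and/or memory B cell derived polyclonal antibodies, HAI, MN titers affect the boost responses". The outcomes are the "boost responses of CD4, memory B cell derived polyclonal antibodies, HAI and MN titers after vaccination". The predictor list and the outcome list name the same four markers: CD4, memory B cell derived polyclonal antibodies (MpAb), HAI and MN. Baseline HAI against HAI boost, baseline CD4 against CD4 boost, and so on are therefore within the plan.

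There is one baseline draw. Section 8.2 says "A serum sample will be obtained from an arm vein for baseline antibody titers" and schedules one PBMC sample at the same visit. CD4 is measured on "PBMCs collected prior to and on day 3, 7, 14 and 180 after vaccination". Serum is drawn at Days 0, 28 and 180.

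Section 12.4 gives no null value other than zero, no reliability correction and no mention of regression to the mean. Its only control for baseline is a difference-in-difference term, and that serves the comparison between vaccine groups.

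**The concern.** When predictor and outcome are the same marker, the Day 0 measurement appears in both, with opposite signs. A subject whose Day 0 assay reads too high gets a high baseline and, for that reason alone, a low boost. A correlation tested against zero counts this as evidence that baseline immunity suppresses the response.

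The question is a live one in this protocol. Section 3.1 says that responses are lower in people who start with higher titres and that the mechanism by which prior exposure acts is unknown. Section 3.3 adds that "Recent studies have emphasized the potential negative effect of vaccination in prior years on both the immune response". A baseline-boost correlation would naturally be read in that light, but the planned test cannot separate a real negative relation from the artefact, and it overstates any real one. The bias also grows with assay noise, so a larger negative r for one marker may only mean a noisier assay.

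**Working it through.** **Plan's own figure.** None exists on this point. The only power figure, in Section 12.2, concerns group differences in CD4 counts. I take its 45 subjects per group as n, because Section 12.4 does not say how many subjects enter the correlations.

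**Which pairs.** Four baselines by four boosts give 16 pairings. Four of them are same-marker.

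**Model with no effect of baseline (log2 scale).** Let T be the true baseline with SD s. Let B be the true boost with SD b, independent of T. Each measurement carries an independent error with SD e.

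- Observed Day 0: x = T + e0
- Observed post: y = T + B + e1
- Boost: y − x = B + e1 − e0
- Cov(x, y − x) = −e²
- r = −e² / √[(s² + e²)(b² + 2e²)]

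The documents give none of s, b or e. I assume s = 2 log2 and e = 0.7 to 1.0 log2. Day 0 reliability s²/(s² + e²) is then 4/4.49 = 0.89 to 4/5 = 0.80. Three values of b are shown.

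| True boost SD b | r at e = 0.7 | r at e = 1.0 | False positives, Fisher z, n = 45 | Same, simulated |
|---|---|---|---|---|
| 0 (identical in everyone) | −0.49/√(4.49 × 0.98) = −0.23 | −1/√(5 × 2) = −0.32 | 34% to 56% | 34% to 57% |
| 1 log2 | −0.49/√(4.49 × 1.98) = −0.16 | −1/√(5 × 3) = −0.26 | 19% to 40% | 19% to 41% |
| 2 log2 | −0.49/√(4.49 × 4.98) = −0.10 | −1/√(5 × 6) = −0.18 | 10% to 22% | 11% to 23% |

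The nominal rate is 5%, and the two-sided critical |r| at n = 45 is 0.294. Fisher z example for b = 0, e = 1: atanh(0.316) × √42 = 2.12, and Φ(2.12 − 1.96) = 56%. More subjects make it worse: at n = 90 the first row becomes 60% to 86%.

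**Does taking a maximum matter?** Little. With reliability 0.8 and boost SD half the observed baseline SD, taking the maximum of one, two or four post values gives r = −0.25, −0.26 and −0.27, with rejection 39%, 40% and 45%.

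**HAI-like data.** Two-fold titres with undetectable set to 1:2, and an assumed error SD of 0.5 to 1 log2, give r = −0.11 to −0.31 and rejection 11% to 58%.

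**Boundary checks.**
- Perfectly measured baseline: r = 0, rejection about 5%.
- Cross-marker pairs with independent errors: r about 0, rejection 4% to 6%.
- A separate Day 0 replicate as predictor, not the value subtracted: r about 0, rejection 4% to 6%.

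**Two repairs that fail.**
- *Uncorrected slope against 1.* If y on x has slope β, then y − x on x has slope β − 1 with identical residuals. Testing β = 1 is therefore the same t-test as r = 0. With no true effect the expected slope is the reliability, 0.89 to 0.80, not 1.
- *Change against the mean of pre and post.* With boost SD 1 to 2 log2 this gives r of about +0.13 to +0.39, falsely significant in about 14% to 77% of trials at n = 45.

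**The case against.** The best case for leaving the plan alone has four parts.

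- *Reach.* The sentence joins the baseline markers with and/or and does not single out same-marker pairs. The one correlation listed as an outcome, in Section 4.2.2, sets CD4 ELISPOT against antibody titres. The regression of HAI or MN boost on CD4 specificities in Section 12.4 is also cross-marker. This stands, and it limits the point to four pairings. It does not remove them, since the two lists match.
- *Size.* The artefact depends on reliability and boost variation, which the documents do not give. The 34% to 57% row needs every true boost to be identical, which is an extreme. This stands, hence the range.
- *A real relation is expected.* Section 3.1 predicts a lower response at higher baseline. This stands too: a reader might infer that any negative correlation found here would be spurious, and the documents do not support that.
- *Importance.* A reader might infer that the repeated-vaccination objective is biased. Section 3.3 addresses that objective by vaccine history and re-enrolment, not by this correlation, and the protocol ranks it as tertiary or exploratory.

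A reader might also quote r = −0.71 or −0.50, which follow from −√[(1 − ρ)/2] for equal pre and post variances with ρ = 0 or 0.5. These are not measures of the artefact. With an error-free baseline, the same conditions mean that boost truly falls as baseline rises.

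Finally, HAI and MN are related markers, which might suggest that their cross-pairs are biased. They are biased only if the Day 0 errors themselves are shared.

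**Conclusion.** The point holds for same-marker pairs. The analysis as written tests against a null that is wrong whenever the Day 0 value carries assay error or short-term within-subject variation, and nothing else in Section 12.4 corrects it.

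Under the assumed SDs and n = 45, the spurious r runs from about −0.10 to −0.32 and the false-positive rate from about 11% to 57%, depending mainly on how much true boosts vary. These figures rest on a true titre SD of 2 log2, an error SD of 0.7 to 1.0 log2, independent errors, and true boost independent of true baseline. The artefact shrinks to nothing as baseline reliability approaches 1.

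The documents do not support extending it to the primary mean-change outcomes, the vaccine-group comparisons, the listed CD4-antibody correlation, or cross-marker pairs with independent assay errors. As a flaw in a supporting analysis, it deserves a modest-priority correction.

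**What to change.** In Section 12.4:

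1. Restrict simple Pearson or Spearman correlations with boost to cross-marker pairs.
2. For same-marker pairs, state that r = 0 is not the null. Regress log post-vaccination value on log Day 0 value, with arm and an arm-by-baseline term. Correct the baseline slope for Day 0 measurement error, using existing assay-replicate or validation data and within-arm reliability. Compare the corrected slope with 1. If no such data exist, report the corrected slope over a stated range of reliabilities.
3. Alternatively, use a predictor whose error is independent of the subtracted value. This can be a replicate Day 0 assay where one is available, or baseline MN for HAI boost and the reverse. Both remove assay error, but not variation that belongs to the single Day 0 sample.
4. Do not substitute an uncorrected slope tested against 1, or the correlation of change with the pre/post mean.

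The cost is a change of wording, a little extra analysis and a wider interval. No new blood draws are needed. Running new replicate assays would add laboratory work; the range-of-reliabilities option avoids it.

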8.3.4 Day 28 visit (\pm 2 days)

Subjects will return for follow up approximately 28 days after vaccination for assessment of the immune response. At that visit, the following procedures will be performed:

- Interval medical history will be obtained including concomitant medications, reviewing any new events since the last visit
-

-
- If indicated by medical history, a directed physical exam will also be performed.
 - Any adverse events (AE) will be recorded as described in the safety section 10.1 and appropriate corrective actions taken if indicated
 - A serum sample will be obtained from an arm vein for antibody titers
 - Peripheral Blood Mononuclear Cells (PBMC) will be collected from an arm vein for assessment of the B cell response to vaccination

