Various parametric or nonparametric mixed-effects regression approaches will be used to study the dynamic curve of each outcome, to take account of the correlation among observations from the same subjects over time. Group indicator will enter the model as a predictor and thus can be compared simultaneous at each time point and also by difference from difference approach to control the effect of baseline values. Demographic information may be controlled by entering the model as predictors. To further investigate the effect of CD4 cell specificity in helping neutralizing antibody responses, regression analysis will be applied, with boost or fold increase of HAI or MN titers as responses, all the CD4 cell specificities as predictor, possibly adjusting demographic variables. Type I and III sum of squares and standard coefficient estimates can be used to compare the effect of CD4 specificities in helping neutralizing antibody responses. The parametric or nonparametric mixed-effects regression approaches may also be used to compare the effects to take account of within-subject correlation. Among-group plasmablast comparisons will be proceeded by: 1). One-way ANOVA, or its nonparametric analog of Kruskal-Wallis test; 2). Repeated ANOVA or its nonparametric analog of Friedman test for simultaneous pairwise comparison, with within-subject correlation taken into account.

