19 SUPPLEMENT/APPENDICES

Table of study procedures

Procedure	Study Day (numbers denote blood volume in mL)							Day 0-56 Blood Volume
	d-21 to 0	0	3	7	14	28	180	
Informed Consent	X							
Medical History	X							
Interval History		X	X	X		X	X	0
Directed Physical Exam*		X	X	X	X	X	X	0
Urine Pregnancy Test**		X						0
Review Entry Criteria	X	X						0
Serum for antibody		10				20	10	30
PBMC for B cells		30		60		60		150
PBMC for CD4 T cells		100	50	80	50		50	280
Randomization		X						
Vaccination		X						
AE review			X	X		X	X	
Total		140	50	140	50	80	60	460
*Examination if indicated by history								
**Female subjects only

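### Section 12.4 should state a group-by-visit model, adjust for the Day 0 value rather than subtract it, and read the vaccine contrast at Day 28 (HAI, MN) and Day 14 (CD4)

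*Combined protocol and SAP*

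**What the plan says.** Section 4.2.1 sets two primary quantities: mean change in HAI and MN titer "from Day 0 to Day 28", and mean change in CD4 ELISPOT reactivity from Day 0 to Day 14.

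Section 12.4 offers two routes to a group comparison of these outcomes.

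- **Summary statistics.** The endpoint is the maximum response, the maximum boost (highest value after Day 0 minus Day 0) or the maximum fold increase. It is compared by ANOVA or t-test, with rank tests as alternatives.
- **Mixed models.** "Various parametric or nonparametric mixed-effects regression approaches will be used to study the dynamic curve of each outcome". Then: "Group indicator will enter the model as a predictor and thus can be compared simultaneous at each time point". The same sentence adds a second contrast, a difference in differences, whose stated purpose is to allow for baseline.

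No model equation is given. The text does not say whether time is categorical or continuous, whether Day 0 is a response or a covariate, or whether the group effect may vary with time. Neither Day 14 nor Day 28 is mentioned in 12.4.

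For CD4, Section 9.2.1 states: "PBMCs collected prior to and on day 3, 7, 14 and 180 after vaccination will be evaluated". Serum is drawn on Days 0, 28 and 180 (Sections 8.2, 8.3.4 and 8.3.6; the row "Serum for antibody" in the Section 19 table).

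**The concern.** The sentence derives a visit-by-visit comparison from the presence of a group indicator. That does not follow unless the group effect is allowed to change over time, and no such term is named. As written, two statisticians could fit different models and both claim to follow 12.4.

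The larger issue is what is estimated and how baseline is handled. The primary windows are not attached to any analysis. The boost, the fold increase and the difference in differences all subtract the Day 0 value. Subtraction removes the effect of baseline only if a one-unit difference at Day 0 carries through as one full unit at follow-up. Section 3.1 describes the opposite: subjects who start high rise less. Section 3.2 reports that in the first full year pre-vaccination titers were highest in the Fluzone group, and that prior vaccination was 18/22 (82%) for Fluzone, 16/22 (73%) for Flublok and 13/26 (50%) for Flucelvax. Given such a gap, a change score tends to favour the arm that starts lower. In that year's comparison of rHA with egg-grown vaccine, the lower-starting arm was the rHA arm.

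**Working it through.** The plan gives no figure for the mixed model, so there is none to reproduce. The power statement in Section 12.2 concerns a two-sample t-test. Only its 45 per group is used here.

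**1. What a group main effect can deliver.** Write the mean for group g (0 or 1) at time t as a(t) + γg. The group difference is γ at every t, Day 0 included. The difference in differences is γ − γ = 0. So neither contrast named in the sentence can be estimated from a main effect. With a group-by-visit term the difference is γ(t), and both exist. As an illustration with assumed effects, take a true CD4 difference of 0.30 at Day 14 and none at Days 0, 3, 7 and 180. A main-effect model with Day 0 among the responses gives 0.30/5 = 0.06 (0.057 in simulation). The group-by-visit model gives 0.297 at Day 14.

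**2. Link to the primary windows.**

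| Outcome | Primary window (4.2.1) | Maximum in 12.4 is taken over |
|---|---|---|
| HAI, MN | Day 0 to 28 | Days 28, 180 |
| CD4 | Day 0 to 14 | Days 3, 7, 14, 180 |

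For serum, the maximum boost equals the Day 28 change unless Day 180 is higher. For CD4 it is the best of four visits, which is a different quantity from the Day 14 change. Only the mixed model could return the primary contrasts directly, and it does not name them.

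**3. What differencing leaves behind.** Assume equal variances at both visits and correlation ρ. Suppose one arm starts d0 higher. The expected follow-up gap due to baseline alone is ρ·d0, so the error in the estimated effect is:

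- change score: ρ·d0 − d0 = −(1 − ρ)·d0;
- unadjusted follow-up value: +ρ·d0;
- Day 0 as covariate: 0.

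At ρ = 0.5 the change score understates the higher-starting arm by half of the gap; at ρ = 0.7, by three tenths. The text of Section 3.2 gives no size for the titer gap, so this is not converted to a titer ratio. Averaged over all possible randomisations the error is zero. It applies to the imbalance actually observed.

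**4. Precision.** Assumed: effect 0.5 SD, ρ = 0.5 or 0.7, two-sided 0.05. From Section 12.2: 45 per arm. With the SD set to 1, the variance per subject is 2(1 − ρ) for the change score and 1 − ρ² with Day 0 as covariate. The standard error is √(variance × 2/45).

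| ρ | Analysis | Variance | SE | 0.5/SE | Power |
|---|---|---|---|---|---|
| 0.5 | change | 1.00 | 0.211 | 2.37 | 65% |
| 0.5 | covariate | 0.75 | 0.183 | 2.74 | 77% |
| 0.7 | change | 0.60 | 0.163 | 3.06 | 86% |
| 0.7 | covariate | 0.51 | 0.151 | 3.32 | 90% |

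Power is from the noncentral t distribution. The covariate rows allow for a chance Day 0 difference between arms. A mixed model with a common Day 0 mean and an unstructured covariance has essentially the covariate row's precision.

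**The case against.** The case against is substantial, and most of it stands.

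- **The model may be what it should be.** A reader might infer that the plan enters group and nothing else, so that the result is one shift averaged over all visits, Day 0 included. Under that reading, with the 0.5 SD effect, 45 per arm and ρ = 0.5, power would be 16% to 48%. The documents do not support this. They never say that group is the only term or that the curves are parallel. The same sentence promises comparison by time point and a difference in differences, which would be identically zero under parallel curves. The fair reading is loose wording for group-specific profiles, and those power figures are not a property of the plan.
- **Curves through few visits.** A reader might also infer that an antibody curve through three serum days could put a peak where no sample exists. No quadratic, line or other form is proposed, and the curve may simply mean the mean profile over scheduled visits.
- **Baseline is not ignored.** Boost, fold increase and difference in differences all address it. 12.4 also compares arms within pH1N1 serostatus groups and plans correlations of baseline with boost. The serostatus split helps little: Section 3.2 reports few subjects at or below 1:8, so most fall in one group where titers still vary. The correlations describe the dependence on baseline but do not adjust the vaccine contrast. The optional adjustment in the mixed model is for demographics.
- **Stratification.** Randomisation is now stratified by prior vaccination (Section 5). This reduces imbalance in history but does not fix the Day 0 titer.
- **Role of the model.** Section 12.2 powers the study on a t-test and calls the study explorative. The mixed model supports that comparison, which limits the seriousness.

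**Conclusion.** The point holds as a cheap improvement; it does not show that the planned analysis is wrong. Three things are established from the text: 12.4 names no group-by-time term although both of its stated contrasts need one; nothing in 12.4 is tied to Day 28 for HAI and MN or to Day 14 for CD4; and the measured Day 0 value is controlled in the vaccine comparison only by subtraction, despite the plan's own account that response depends on it and that the arms differed.

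The illustrative gain from adjusting is about 12 percentage points of power at correlation 0.5 (77% against 65%) and about 4 at 0.7 (90% against 86%). It also removes an error of 0.5 or 0.3 times any observed Day 0 gap. The effect size, the correlations and the equal variances are assumptions. The gain shrinks as the correlation approaches 1.

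**What to change.** In Section 12.4, replace the sentence on the group indicator with text to this effect: *Visit enters as a category, with a group-by-visit interaction and a stated within-subject covariance (unstructured where it can be fitted). Randomised arms share a common Day 0 mean, or Day 0 enters as a covariate; this replaces the difference in differences. The vaccine contrast is read at Day 28 for HAI and MN and at Day 14 for CD4. Other visits are secondary.*

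Add two conditions:

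- Repeat participants receive the vaccine they had before (Sections 5 and 8.2) and are not randomised again. Their Day 0 values may already carry a vaccine effect, so repeat-year data should not share the common Day 0 mean.
- If seasons are pooled, the common Day 0 mean should hold within season and prior-vaccination stratum, because the set of arms changed over time (Section 3.2).

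The maximum-response comparisons can stay as supporting analyses.

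Cost: wording and a few more model parameters. No new samples, visits or assays are needed.
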